Data collection for all subjects will be conducted in the BioMotion Laboratory the CCTS and the MRISC at the University of Kentucky. Testing sessions may last approximately 6 hours depending on scheduling of the MRISC and CCTS procedure room. Subjects will be requested to wear sports clothes (e.g. athletic shoes, shorts, and t-shirt). The first data collection will occur before they start the treatment program and will consist of all study procedures except running and jumping. The second data collection will occur before surgery and will consist of measuring intake scales, quadriceps strength, and walking gait. Following surgery, subjects will be administered the intake questions at regular intervals to help the study staff assist them with attending their physical therapy visits. We will then administer all study interventions except running and jumping between 3-4 months after surgery. The last data collection will occur 6-7 months after surgery and will include quadriceps strength assessment, walking and running gait, step down test performance and jumping. The timing of testing maybe delayed by upto 1-2 weeks if the subject is out of town for vacation or illness.

Research procedures for the muscle biopsy and MRI arm of the study will follow procedures already within another study focused on subjects with an ACL tear and reconstruction (11-0388):

Patients will be asked to stop taking aspirin 5 days and NSAIDS 3 days prior to starting the study. Study personnel will confirm that they have not taken aspirin or NSAIDS prior to the start of the muscle biopsy. Those who do not will be excluded from the additional analysis.

Muscle Biopsy: A muscle biopsy sample will be obtained from the vastus lateralis of both thighs in individuals before surgery and again when they have been cleared to practicing drills for their sport or are in a maintenance phase of physical therapy. The muscle biopsy procedure will proceed as follows for each subject taking approximately 15 minutes.

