In addition, standard venipuncture methods will be used to collect one 7.5 mL tube of blood to be used for analysis at both biopsy collection times and one week post surgery. Blood samples will be spun at 3500 RPM for 10 minutes and the serum will be frozen at -80°C. Samples will be stored and archived in the UK-Orthopaedics Serum repository for analysis. Samples can be destroyed if a subject requests this.

Diffusion Tensor imaging magnetic resonance imaging (DTI-MRI) routine turbo spin echo images for muscle volume, as well as T1 rho and T2 mapping sequences maybe run depending on time and investigator judgement on a 3T Siemens Magnetom Trio MRI scanner (Siemens Medical Solutions USA, Inc., Malvern, PA), at the University of Kentucky's Magnetic Resonance Imaging and Spectroscopy Center (MRISC). DIXON VIBE will be used to assess fat content of the thigh and vastus lateralis muscle, with CEST imaging to form an association with the degree of fibrosis of the muscle and ASL to estimate blood flow to the muscle. The patient will lay supine with a small bolster placed under their knee. Flexible coils will be placed along the leg and the Quadriceps will be imaged on the involved leg and as time allows the unininvolved leg. Hearing protection will be provided to increase the participants comfort. The DTI images will then be post processed with custom matlab code and muscle properties determined.

3 Day Food Record: We will ask subjects to complete 3 day food record (see attached) before starting the study, prior to and after surgery and then again at 4-5 months post surgery..

Gait Analysis: Small reflective markers will be attached to the subject's skin. Using Raptor cameras (Motion Analysis Corporation) a stationary trial will be collected to identify anatomical landmarks. Motion data at the hip, knee and ankle will be collected for 10 seconds every minute during both walking and running.

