Continuous participant demographic variables (e.g., age, body mass index (BMI), time since surgery) were summarized with descriptive statistics (e.g., sample size, mean, standard error). Categorical variables (e.g., sex assigned at birth) were summarized with descriptive statistics (e.g., counts and percentages). Summary statistics are also presented by treatment group. A chi-squared test was used to evaluate between-group differences in sex assigned at birth and two-sample *t*-tests were used to evaluate between-group differences in quantitative covariates.

All primary and secondary outcomes were continuous. For each outcome, change scores were calculated as: post-intervention (4-5 months post-surgery) – pre-intervention (baseline pre-surgery). Two-sample *t*-tests were then used to assess between-group differences in change scores. Distributional assumptions of two-sample *t*-tests were assessed using plots of each outcome. An analysis of blinding was performed for each of the participants, the data analysts, and the primary investigator of the study. Chi-square tests (or Fisher's exact tests in the case of small cell counts) were used to identify any association between guesses and treatment group for each of the blinded groups. All analyses were performed using R (R version 4.1.2, R Core Team, 2023) and *p*-values ≤ 0.05 were considered statistically significant.

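### The only outcome test, an unadjusted t-test on change scores, is valid but less precise than ANCOVA on the same two measurements unless the baseline slope is close to 1

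*Combined protocol and SAP*

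**What the plan says.** The Statistical Analysis section states that all primary and secondary outcomes are continuous. It defines a change score for each one and says that two-sample t-tests "were then used to assess between-group differences in change scores". The later value is "post-intervention (4-5 months post-surgery" and the earlier one "pre-intervention (baseline pre-surgery" (each with a closing bracket in the original). The other tests in the section compare baseline covariates or examine blinding; none is an outcome model. Data Collection & Research Materials says that a computer randomises participants to the two band pressures.

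The same section sets out the visits. On the first: "The first data collection will occur before they start the treatment program and will consist of all study procedures except running and jumping". A second collection, limited to intake scales, quadriceps strength and walking gait, also falls before surgery but after the programme has begun. On the next full collection: "We will then administer all study interventions except running and jumping between 3-4 months after surgery". The Payment section, like the Statistical Analysis section, refers to a 4-5 month visit.

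Project Information gives a maximum of 55 subjects, and Subject Demographics gives 60.

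**The concern.** Subtracting the baseline is the same as adjusting for it with a coefficient fixed at 1. If the real regression of follow-up on baseline is flatter or steeper than that, the subtraction over- or under-corrects, and the mismatch stays in the estimate as noise. ANCOVA uses the same two measurements but takes the coefficient from the data.

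This matters because the trial is small and some outcomes may have fewer participants still. For the biopsy work, on participants who do not stop aspirin and NSAIDs, the plan says "Those who do not will be excluded from the additional analysis"; some MRI sequences "maybe run depending on time and investigator judgement". At these sizes chance baseline imbalance is not negligible. With 28 and 27 per arm, one standard error of the baseline difference is √(1/28 + 1/27) = 0.27 SD. At a slope of 0.5 and equal SDs, an imbalance of that size moves the change-score difference by (1 − 0.5) × 0.27 ≈ 0.13 SD.

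Two definitions also affect any analysis of these measurements. The baseline must be the collection before training. If it were the second pre-surgery visit, neither method would capture the full effect of the programme. The follow-up window is given in two different ways.

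**Working it through.** **Nothing to reproduce.** The documents state no power, effect size, SD or correlation.

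**Inputs from the documents.** N = 55 or 60; significance at p ≤ 0.05; continuous outcomes; randomised allocation.

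**Assumptions.** 1:1 allocation (28/27 at 55), two-sided testing, and a true effect of 0.6 follow-up SD unless stated. The pre-post correlation ρ is varied. SDs are equal unless stated. Analysed totals of 40 and 24 are illustrative, for outcomes with incomplete collection.

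**Formulas.** Set SD_post = 1, k = SD_post/SD_pre and slope b = ρk.

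- Var(change) = 1 + 1/k² − 2ρ/k = (1 − ρ²) + (1 − b)²/k²
- Var(ANCOVA) = (1 − ρ²) × [1 + 1/(N − 4)], where the bracket is the expected price of estimating the slope

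Apart from that price, the excess variance of the change score is (1 − b)²/k², which is zero only at b = 1. Power comes from the noncentral t distribution with N − 2 degrees of freedom (t-test) and N − 3 (ANCOVA).

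**One case in full: N = 55, ρ = 0.5, k = 1.**

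- Change score: variance 1 + 1 − 1 = 1.000; SE = √(1.000 × (1/28 + 1/27)) = 0.2697; 0.6/0.2697 = 2.22; power 58.9%.
- ANCOVA: variance 0.75 × (1 + 1/51) = 0.7647; SE = 0.2359; 0.6/0.2359 = 2.54; power 70.4%.

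**Power (%), change-score t-test / ANCOVA, equal SDs, effect 0.6:**

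| N analysed | ρ = 0.3 | ρ = 0.5 | ρ = 0.7 | ρ = 0.8 | ρ = 0.9 |
|---|---|---|---|---|---|
| 60 | – | 62.8 / 74.4 | 83.9 / 88.7 | – | – |
| 55 | 45.5 / 62.0 | 58.9 / 70.4 | 80.5 / 85.7 | 93.2 / 95.0 | 99.8 / 99.9 |
| 40 | – | 45.6 / 55.8 | 66.5 / 72.3 | – | 98.5 / 98.7 |
| 24 | – | 29.0 / 35.2 | 44.2 / 48.3 | – | 88.1 / 88.0 |

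At N = 55 and ρ = 0.5, an effect of 0.4 gives 30.8 / 38.4 and an effect of 0.8 gives 82.9 / 91.4.

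**Variance ratio.** At N = 55 with equal SDs, ANCOVA variance divided by change-score variance is 0.66, 0.77, 0.87, 0.92 and 0.97 at ρ = 0.3, 0.5, 0.7, 0.8 and 0.9.

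**Where ANCOVA loses.** With equal SDs the two break even at b = 2/[1 + 1/(N − 4)] − 1, which is 0.965 at 60, 0.962 at 55, 0.946 at 40 and 0.905 at 24. With k = 1.25 and N = 55 the change score is better only for slopes of about 0.88 to 1.09. With k = 0.8 it is never better.

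At b = 1 the expected variance cost of ANCOVA is 1/(N − 4): 1.8% at 60, 2.0% at 55, 2.8% at 40 and 5.0% at 24. In power terms, with ρ = 0.8 and k = 1.25:

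- N = 55, effect 0.4: 68.0% falls to 67.1%
- N = 24, effect 0.6: 64.9% falls to 62.6%

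The cost varies between trials: in 5% of them it exceeds about 7.6% at 55, 11% at 40 and 19-20% at 24.

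**Simulation check.** With 20,000 trials per setting, type I error was 0.047-0.053 for both tests, both estimators were unbiased, and the power cells checked agreed with the formula within about 0.75 points.

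**The case against.** The strongest reply is that the plan contains no error. In a randomised trial the change-score t-test is unbiased and holds its type I error, so this is a choice between two valid estimators. The benefit cannot be established from the documents either: every power figure rests on an assumed correlation, SD ratio and effect, and the gain runs from 16.5 points to nil or slightly below. All of this stands. It limits the claim to precision and makes the table a range, not a forecast.

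A second reply is that the Statistical Analysis section is in the past tense throughout, so the analysis may already have been run. The blinding tests "were used to identify any association between guesses and treatment group", which requires the allocation. Changing the main analysis after seeing results by arm would be worse than the lost precision. This also stands and governs how the fix is applied. The status is not certain, because data analysts are listed among the blinded groups and the project end date is 9/30/2025.

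Third, the advantage of a common-slope ANCOVA assumes near-equal allocation or similar slopes in the two arms, and the allocation ratio is not stated. That is a fair caveat: with both unequal, the cost can be larger than shown.

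Finally, the visit definitions are a separate matter from the choice of test. The word pre-intervention, read with the visit schedule, already points to the first collection, so naming it is a matter of wording. The 3-4 versus 4-5 month mismatch is real. The permitted programme extension of 1-2 months and testing delay of 1-2 weeks soften it but do not say which visit supplies the analysed value.

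**Conclusion.** The point holds as one of precision, not validity. The plan's only between-arm outcome test gives up precision that the baseline measurements could supply, unless the true slope is close to 1. At 55 analysed, with equal SDs and an effect of 0.6 SD, the illustrative gain is about 5 to 17 power points for correlations of 0.7 down to 0.3 and almost nothing at 0.9. At a slope of 1 the loss is about 1 point at 55 and about 2 at 24. The balance therefore favours ANCOVA, but nothing in the documents shows which case applies. This is a recommended improvement at low cost, with medium confidence in how much it would bring.

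**What to change.** For each outcome with a pre-training baseline, regress the post-surgery value on arm and the baseline of that same outcome, with no other covariates. Report the adjusted difference with its 95% confidence interval, and keep the change-score t-test as a sensitivity analysis. If the analysts have already seen results by arm, do the reverse: leave the t-test as the planned analysis and report the ANCOVA as supplementary.

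Add two clarifications to the Statistical Analysis section:

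- State that the baseline is the first data collection, before the treatment programme starts.
- Reconcile the follow-up window between Data Collection & Research Materials (3-4 months) and the Payment and Statistical Analysis sections (4-5 months), so that the post-surgery value is defined.

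The cost is one degree of freedom and one line of R per outcome, plus two sentences of text. No new data are needed. The statistical price is the small expected variance penalty at a slope of 1 shown in the working.
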